7.1.3.2 Vertebral fracture assessments

The lateral spine radiographs will be assessed for vertebral fractures using the Genant Semiquantitative Scoring Method assigning each vertebra a grade between 0 and 3 (SQ score):

- Grade 0: normal
- Grade 1: mild fracture
- Grade 2: moderate fracture
- Grade 3: severe fracture

A new vertebral fracture is defined as an SQ score ≥ 1 at a post baseline visit where the baseline SQ score = 0 for the associated vertebrae. A subject is defined as having a new fracture at a visit if they have at least 1 vertebra with a new fracture.

A worsening vertebral fracture is defined as an increase in SQ score ≥ 1 from the previous visit (where the baseline SQ score > 0) for the associated vertebrae. A subject is defined as having a worsening fracture at a visit if they have at least 1 vertebra with a worsening fracture.

The sum of all grades at a visit is defined as sum of all SQ scores across all vertebrae assessed at a visit by the Genant Semiquantitative Scoring Method.

The below vertebral height parameters (for each vertebra) will be derived from the 6-point vertebral morphometry assessments:

- Anterior /Posterior height ratio (HA/HP)
- Mid / Posterior height ratio (HM/HP)

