8.5.3.3.1 Vertebral Fractures

For all vertebral assessments the X-ray scans will be used as source.

The number and proportion of patients with a new vertebral fracture and new or worsening vertebral fracture will be summarised by treatment group throughout the treatment period (at each visit). In addition, a P-value for the comparison between each group will be provided using a Chi squared test.

The total number of new vertebral fractures and new or worsening vertebral fractures per patient during the treatment period will be compared between each treatment group using a poisson regression model as described in section 8.5.1. An estimate of the ratio of new vertebral fractures and new or worsening vertebral fractures between treatment groups will be presented together with a two-sided 95% confidence interval and P-value.

For patients that have a vertebral fracture a shift table of the change in fracture grade will be presented. The number and percentage of patients with each level of change (from worst baseline grade to worst post-baseline grade) will be displayed.

Finally the total sum of vertebral fracture grades will also be analysed via ANCOVA in the same manner as the change from baseline in Tr.vBMD (radius) on HRpQCT (see Section 8.5.2.1).

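### At Month 12 the new-or-worsening vertebral fracture proportion counts new fractures since baseline but worsening only since Month 6

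*SAP*

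**What the plan says.** SAP 7.1.3.2 grades each vertebra 0 to 3 by the Genant semi-quantitative (SQ) method and then uses two reference points.

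- New: "A new vertebral fracture is defined as an SQ score ≥ 1 at a post baseline visit where the baseline SQ score = 0". The reference is baseline.
- Worsening: "A worsening vertebral fracture is defined as an increase in SQ score" of at least one grade "from the previous visit (where the baseline SQ score > 0) for the associated vertebrae". The reference is the preceding film.

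Patient status is set visit by visit: "A subject is defined as having a worsening fracture at a visit if they have at least 1 vertebra with a worsening fracture". The section has no rule that carries an earlier worsening forward.

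SAP 8.5.3.3.1 takes the number and proportion of patients with a new fracture, and with a new or worsening fracture. It says these "will be summarised by treatment group throughout the treatment period (at each visit"), with a chi-squared test between groups. Separately, "The total number of new vertebral fractures and new or worsening vertebral fractures per patient during the treatment period will be compared" by Poisson regression. The same section plans a shift table from worst baseline to worst post-baseline grade, and an ANCOVA of the summed grades.

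SAP 4.2 (item 8) defines the endpoint as change in vertebral fractures from baseline at 6 and 12 months. The protocol's efficacy table (11.3.1) lists a 2x2 analysis and a Poisson regression for these outcomes, without naming a reference visit. The schedule of activities and Appendix 6 place spine films at baseline, Month 6 and Month 12 during treatment.

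**The concern.** A composite is readable only if its parts cover the same period. At Month 6 they do, because the previous visit is baseline. At Month 12 they do not. A vertebra that newly fractured before Month 6 is still counted, while one that worsened before Month 6 and then stayed stable is not.

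The Month 12 proportion and its test therefore depend on when in the year worsening happened, and not only on whether it happened. Two arms with the same number of patients worse than baseline could show different Month 12 proportions if worsening came earlier in one of them. The result also does not measure the stated endpoint, change from baseline at Month 12.

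**Working it through.** The documents give no rate, power or sample size for the vertebral analyses, so there is no plan figure to reproduce. The definitions can be checked exactly; the size needs assumptions.

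**1. Enumerating grade paths.** Write each vertebra as (baseline, Month 6, Month 12), with grades 0 to 3. There are 4 × 4 × 4 = 64 paths, of which 20 never decrease. Apply the SAP 7.1.3.2 rules at Month 12 and compare them with the same flag when worsening is judged against baseline.

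| Path | SAP flag at Month 12 | Flag against baseline |
|---|---|---|
| 0,1,1 | yes (new) | yes |
| 1,1,2 | yes (worsening) | yes |
| 1,2,2; 1,3,3; 2,3,3 | **no** | yes |
| 2,1,2 | **yes** | no |

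Among the 20 non-decreasing paths, exactly three are worse than baseline at Month 12 but unflagged: 1,2,2, 1,3,3 and 2,3,3. No new fracture present at Month 12 is lost. Over all 64 paths, four are missed (the three above and 1,3,2). Ten are flagged as worsening although Month 12 is not above baseline; in these the grade falls and then rises again, as in 2,1,2.

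**2. Share of worsened vertebrae unflagged.** Assume a vertebra already fractured at baseline has the same chance p of a one-grade rise in each half-year, with grades not falling. Against baseline, the chance of being worse at Month 12 is 1 − (1 − p)². Under the SAP it is p. The flagged share is p / [1 − (1 − p)²] = 1 / (2 − p). For p = 0.03 this is 1 / 1.97 = 0.51, so about half are unflagged. This fraction comes from the equal-risk assumption and barely depends on p.

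**3. Patient level, built from vertebrae.** Assume 13 vertebrae, each fractured (grade 1) at baseline with probability q, and risk p per half-year for a new fracture or a one-grade rise.

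- Against baseline: 1 − (1 − p)^26
- Under the SAP: 1 − [(1 − q)(1 − p)² + q(1 − p)]^13

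| p | q | Against baseline | SAP | Shortfall (points) |
|---|---|---|---|---|
| 0.005 | 0.10 | 12.2% | 11.6% | 0.6 |
| 0.01 | 0.25 | 23.0% | 20.4% | 2.6 |
| 0.03 | 0.25 | 54.7% | 49.9% | 4.8 |
| 0.03 | 0.40 | 54.7% | 46.9% | 7.9 |

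**4. Patient level, assumed directly.** Let pn and pw be independent half-year patient risks of a new and of a worsening fracture. Affected by Month 12: 1 − (1 − pn)²(1 − pw)². Flagged at Month 12 by the SAP: 1 − (1 − pn)²(1 − pw). The last column uses the planned 25 patients per blinded arm.

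| pn | pw | Affected | Flagged | Shortfall (points) | Patients of 25 |
|---|---|---|---|---|---|
| 0.05 | 0.05 | 18.5% | 14.3% | 4.3 | 4.6 v 3.6 |
| 0.05 | 0.10 | 26.9% | 18.8% | 8.1 | 6.7 v 4.7 |
| 0.10 | 0.10 | 34.4% | 27.1% | 7.3 | 8.6 v 6.8 |
| 0.10 | 0.20 | 48.2% | 35.2% | 13.0 | 12.0 v 8.8 |

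Across both sets the shortfall runs from 0.6 to 13 points. Every p, q, pn and pw, and the 13 vertebrae, are assumptions.

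**The case against.** The strongest reply is that nothing is lost overall. Worsening by Month 6 is reported and tested at Month 6. In the treatment-period total, a comparison with the previous visit counts each step in the interval where it occurs, so 1,2,2 is included. Incidence within an interval is a legitimate quantity. The shift table and the summed grades keep the comparison with baseline. The same rule applies to every arm, so a distorted contrast needs timing that differs by arm. The magnitudes are assumed.

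Much of this stands, and it limits the point to the Month 12 composite flag and its test. It does not remove it. Interval incidence would be coherent if both parts used it, but here only one does. The shift table uses each patient's worst grade, so a rise in a milder vertebra can be hidden, and the summed grades are a different outcome; neither changes the chi-squared result. The words about the whole treatment period in 8.5.3.3.1 might suggest a cumulative display, but the text specifies each visit and gives no carry-forward rule.

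A reader might go further and infer that the Poisson total counts a persisting new fracture twice, once at each visit. The documents do not support that as a finding. SAP 8.5.3.3.1 counts fractures per patient over the period, and nowhere does the plan say that visit flags are added. Double counting would come from a programming choice that the SAP neither makes nor rules out.

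**Conclusion.** Wrong as written, minor, and confined to a secondary endpoint. That the Month 12 composite mixes a twelve-month count of new fractures with a six-month count of worsening follows from the definitions and needs no assumption. So does the mismatch with an endpoint defined as change from baseline.

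The size does rest on assumptions. About half of worsened vertebrae are unflagged if risk is equal in the two half-years; more if worsening comes early, fewer if late. The patient-level shortfall of about 0.6 to 13 points is a range over illustrative risks, not a prediction. No bias between arms has been shown. The Month 6 results, the new-fracture results at either visit and the primary HRpQCT analysis are unaffected. For the period total, the plan lacks only a clarifying sentence.

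**What to change.** In SAP 7.1.3.2, define worsening, like new, against the baseline grade for the Month 6 and Month 12 flags. In SAP 8.5.3.3.1, add a clarification that the treatment-period total counts each new fracture once, and state how repeated worsening of one vertebra (such as 1, 2, 3) is counted. Counting it as one event or as two steps is defensible either way, but the choice should be written down before unblinding. If worsening since the previous visit is also of interest, it can be shown as a separately labelled summary.

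The cost is a few sentences and one derivation. No extra films or reads are needed, and the chi-squared and Poisson methods stay as they are.

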Secondary	
 • Tr. vBMD (tibia): An ANCOVA will be calculated on log transformed data as described above on the FAS, mFAS, the PP population, the FAS and the Non-Restricted FAS in both versions • DXA BMD: Changes will be compared treatment groups using an ANCOVA as described above on the percent change from baseline and on the T-scores for the following variables on the FAS, the PP population, the FAS and the Non-Restricted FAS in both versions: 
 ○ Lumbar BMD ○ Whole body BMD ○ Proximal femur BMD • Vertebral assessments: 
 ○ Vertebral fractures assessed by Genant's semi-quantitative method: 
 ▪ 2x2 table analysis for occurrence of new and new or worsening fractures (yes/no) ▪ Poisson regression for number of new and new or worsening fractures, if appropriate

Endpoint	Statistical Analysis Methods
	
 ▪ Shift tables to investigate the change in grade for existing fractures ▪ An ANCOVA with baseline value as covariate and treatment group and stratum as factors to investigate the percent change from baseline in numbers of vertebral fractures ▪ An ANCOVA with baseline value as covariate and treatment group and stratum as factors to investigate the total sum of vertebral gradings 
 ○ Vertebral height derived from 6-point quantitative morphometry: The maximum change from baseline in the H_A/H_P and the H_M/H_P ratio for fractured vertebrae will be analysed using ANCOVA • Change in bone histomorphometry • HRpQCT parameters: 
 ○ Total vBMD ○ Cortical vBMD ○ BV/TV ○ Met/Inn ○ TbTh ○ TbN ○ Inhomogeneity ○ Cortical thickness ○ Cortical porosity (tibia and radius) • Body composition: Comparisons between treatment groups will be performed using an ANCOVA as described above 
 ○ Body height ○ Body weight ○ BMI ○ Lean body mass ○ Fat body mass • Change from baseline to each visit for bone turnover markers and metabolic biomarkers • Fracture rate: Chi square tests will be calculated to assess differences across treatment groups on the following on the FAS, the PP population, the FAS and the Non-Restricted FAS in both versions: 
 ○ Total fracture rate ○ Peripheral fracture rate

Endpoint	Statistical Analysis Methods

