7.2 Handling of missing data and outliers

7.2.1 Missing data analysis methods

Unless specified, data in summary tables will be presented using Observed Case (OC) data and therefore no missing data will be imputed.

For data listings, unless specified, all data will be presented as they have been recorded (e.g. missing and partial dates will not be replaced).

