8.5.3.3.2 Vertebral Height

Vertebral height derived from 6-point quantitative morphometry will be summarized at 6 and 12 months. The mean (across all vertebrae) Anterior, Mid and Posterior heights, HA/HP ratio and HM/HP ratio will be summarised descriptively.

The maximum change from baseline in the HA/HP and the HM/HP ratio for fractured vertebrae will be analysed using ANCOVA in the same manner as the change from baseline in Tr.vBMD (radius) on HRpQCT (see Section 8.5.2.1).

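### The vertebral grade total uses no common set of vertebrae across visits, and the shift table follows each patient's worst grade instead of the fractures present at baseline

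*SAP*

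**What the plan says.** **Grade total.** SAP 7.1.3.2 grades each vertebra from 0 to 3 and then states: "The sum of all grades at a visit is defined as sum of all SQ scores across all vertebrae assessed at a visit". It names no vertebral range, no minimum number of levels read, and no rule for a level that cannot be read. SAP 7.2.1 says that, unless specified, "data in summary tables will be presented using Observed Case (OC) data and therefore no missing data will be imputed", and SAP 7.2.2 has no vertebral rule. SAP 8.5.3.3.1 adds: "Finally the total sum of vertebral fracture grades will also be analysed via ANCOVA in the same manner as the change from baseline" in radial Tr. vBMD. Protocol 11.3.1 also plans an ANCOVA of the total and sets no completeness rule.

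**Shift table.** Protocol 11.3.1 plans: "Shift tables to investigate the change in grade for existing fractures". SAP 8.5.3.3.1 builds the table per patient, for patients who have a vertebral fracture, "from worst baseline grade to worst post-baseline grade". SAP section 9 declares no change from the protocol.

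**Heights.** SAP 8.5.3.3.2: "The mean (across all vertebrae) Anterior, Mid and Posterior heights, HA/HP ratio and HM/HP ratio will be summarised descriptively".

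**Related rules.** SAP 7.1.3.2 also defines new and worsening fractures by comparing a vertebra with itself, and SAP 8.5.3.3.1 tests these by Chi squared test and Poisson regression. For HRpQCT, SAP 7.1.3.1 uses only the region common to all of a patient's scans.

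**The concern.** A change in a sum means something only if both sums cover the same items. Here they need not. Under observed-case handling, an unread vertebra contributes nothing to the total, which is the same as grading it normal. If it carried a fracture grade at baseline, the total falls and the spine looks better. If it was unreadable only at baseline and carries a grade later, the total rises and the spine looks worse.

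Lost levels are plausible in this population. Protocol 4.1 lists scoliosis as a disease feature, and inclusion criterion 3 accepts a vertebral fracture in the past 5 years as a qualifying event. Vertebral endpoints are analysed on the FAS and PP populations, in which every arm receives setrusumab. No untreated arm could therefore show how far a within-arm change comes from film quality.

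The shift table has a different fault: it answers a question the protocol did not ask. It follows a patient's maximum, which may sit in one vertebra at baseline and in another later, and it has a ceiling in the patients with the most severe disease.

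**Working it through.** The documents state no power, rate or expected value for these analyses, so there is no figure to reproduce. The SAP definitions are applied to example spines. Assumed, not in the documents: 13 vertebrae read, the example grades, and the rates of loss. From the documents: grades 0 to 3, and 25 participants per arm.

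**1. Losing one vertebra, no true change.** Baseline grades 3, 2, 1, 1 and nine zeros; total 3 + 2 + 1 + 1 = 7.

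| Vertebra unreadable later | Total as defined | Change | Change over vertebrae graded at both |
|---|---|---|---|
| grade 3 | 4 | -3 | 0 |
| grade 2 | 5 | -2 | 0 |
| grade 1 | 6 | -1 | 0 |
| grade 0 | 7 | 0 | 0 |

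**2. Loss together with true progression.** Same spine; the grade 2 vertebra is unreadable and one grade 1 vertebra goes to 2. As defined: 7 to 3 + 2 + 1 = 6, change -1. Over the common set: 3 + 1 + 1 = 5 to 6, change +1. The sign reverses.

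**3. Size in an arm.** If 2 of 25 patients each lose one vertebra of grade 2 or 3, the arm mean moves by 2 × 2/25 = 0.16 or 2 × 3/25 = 0.24. One new grade 1 fracture adds 1/25 = 0.04, so the shift offsets 4 to 6 of them in the mean total.

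More generally, take a baseline total S, all levels read at baseline, and a chance p that a graded vertebra is unreadable later. The expected spurious change per patient is -p × S:

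| S | p = 2% | p = 5% | p = 10% |
|---|---|---|---|
| 3 | -0.06 | -0.15 | -0.30 |
| 7 | -0.14 | -0.35 | -0.70 |
| 12 | -0.24 | -0.60 | -1.20 |

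**4. Within and between arms.** With true changes A and B in two arms and the same spurious loss d in each, the observed within-arm changes are A - d and B - d. The difference is (A - d) - (B - d) = A - B. Equal loss cancels between doses and stays in each arm's own change.

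**5. Shift table ceiling.** Baseline 3, 1, 1, 0 becoming 3, 2, 2, 1: worst grade 3 to 3, shown as no change. The total goes from 5 to 8, with two worsened vertebrae and one new fracture.

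Counting every possible progression of a single vertebra in a 13-level spine, these leave the worst grade unchanged:
- baseline worst 3 (grades 3, 2, 1, 1): 32 of 32;
- baseline worst 2 (grades 2, 1, 1): 22 of 35;
- baseline worst 1 (one graded vertebra): 12 of 38.

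These are counts of possibilities, not probabilities.

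**6. Mixing.** Baseline 1, 0 becoming 1, 2: the table shows 1 to 2, although the existing fracture did not change and the grade 2 is a new fracture elsewhere.

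**The case against.** **Progression is caught elsewhere.** A reader might infer that the vertebral analysis as a whole hides progression. It does not. New and worsening fractures are defined and tested vertebra by vertebra, so the spine in step 5 counts there as one new and two worsening fractures, and the grade 1 fractures offset in step 3 would still be counted. This stands, and confines the fault to the total and the shift table.

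**Direction and rate are unknown.** A reader might also infer that lost vertebrae always flatter the drug. The documents do not support that. A lost grade 0 level changes nothing, a level unreadable only at baseline biases the other way, and long-standing scoliosis may hide the same level at every visit. This stands.

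**The effect on a test may be small.** Two patients at -3 and 23 at 0 give mean -0.24, SD 0.83, SE 0.83/√25 = 0.166, t about -1.44 and p about 0.16 in a one-sample t-test. The example would not by itself produce a significant result. It is also uncertain that the total is tested against zero. The cross-reference to SAP 8.5.2.1 permits it, but SAP 8.1.4 ties that test to the primary analysis and describes pairwise comparisons for secondary endpoints. This stands too; the within-arm change remains biased as an estimate.

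**Heights.** The mean heights are descriptive only. The height ratios tested by ANCOVA are derived per vertebra. This stands.

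**Imaging Charter.** Protocol 10.1.1.3 refers to it for both reading methods. It may fix the levels read, but the SAP cites no such rule for the total.

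**Protocol wording.** Protocol 11.3.1 does not require a vertebra-level table in so many words. However, a table of patient maxima cannot show what happened to fractures already present.

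**Conclusion.** Both rules, followed as written, give misleading results in identifiable cases. A lost vertebra of grade 1 to 3 moves a patient's total by 1 to 3 with no change in bone, and a patient whose worst baseline grade is 3 can never shift upward in the table. The table also departs from the protocol's stated purpose without being declared in SAP section 9.

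The real size is unknown. The arm-level shift of 0.16 to 0.24 rests on an assumed loss in 2 of 25 patients, and the net direction is not fixed. Between-dose comparisons are largely protected if readability and baseline totals are similar across doses; within-arm change is not.

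This concerns supporting secondary analyses without multiplicity adjustment. The vertebra-level fracture analyses, the primary Tr. vBMD analysis and the sample size do not depend on either rule. The change is worth making because it is cheap and applies to vertebrae the principle the SAP already uses for HRpQCT.

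**What to change.** **SAP 7.1.3.2 and 8.5.3.3.1, grade total.** For each post-baseline visit, compute the sum of grades at baseline and at that visit, and the change, only over vertebrae graded at both. Use that matched baseline sum as the ANCOVA covariate. Report per arm and visit how many vertebrae were dropped, with their baseline grade where one was read.

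**SAP 8.5.3.3.2, heights.** Apply the same restriction to the descriptive mean heights and mean ratios.

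**SAP 8.5.3.3.1, shift table.** Replace the worst-to-worst table with a vertebra-level table, baseline grade by visit grade, for vertebrae with baseline grade 1 or more. New fractures remain in their own analysis. If the patient-level table is kept as an addition, declare it in SAP section 9.

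**Cost.** SAP wording and programming; grades are already assigned per vertebra, so no new data are needed. A vertebra unreadable at one visit no longer contributes to that comparison. The restriction does not cure informative loss: a vertebra that became unreadable because it collapsed would still drop out, which is why the dropped count and baseline grades must be shown.

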7.1.3.3 Time to first fracture

The time to first fracture for each fracture category (Total, Peripheral, Vertebral, Non-vertebral and Long-bone) is defined as the time (in days) from the date of first dose of active study medication until the date of date of diagnosis (defined as first occurrence of symptoms of fracture) of each specific fracture type.

Patients who do not have a fracture will be censored at the date of completion/discontinuation of the treatment period for each category.

7.1.3.4 Short Form 12 Health Survey (SF-12)

SF-12

The SF-12 is a generic, 12-item survey that measures 8 domains of health: physical functioning, role limitations due to physical health, bodily pain, general health perceptions, vitality, social functioning, role limitations due to emotional problems, and mental health. It yields scale scores for each of these 8 domains and 2 summary measures of physical and mental health: The Physical Component Summary and the Mental Component Summary. Please see Appendix A **Error! Reference source not found.** for detailed scoring of each domain and component scores.

7.1.3.5 5-level descriptive system (EQ-5D-5L)

EQ-5D-5L

The EQ-5D-5L is a standardised measure of health status comprised of a descriptive system of 5 health-related quality of life states (i.e., mobility, self-care, usual activities, pain/discomfort, and anxiety/depression) and a Visual Analogue Scale (VAS) of overall health.

Each dimension is rated on a 5-point response scale indicating severity of problems, where 1 is “no problems” and 5 is “extreme problems”. The 5 questions are scored and together contribute to the EQ-5D index (utility) score between 0 and 1 (1 being perfect health), which will be calculated using the developers’ algorithm based on country-specific reference score sets. Please see Appendix B for detailed scoring of the EQ-5D index score.

The EQ-5D VAS is a measure of overall self-rated health status, used and analysed separately from the index score. The VAS ranges from 0 to 100, with higher scores indicative of better overall health.

